2.4.2. Benefits to society

This study may identify a useful medication that will benefit patients with islet transplantation.

3. OVERALL STUDY DESIGN AND PLAN DESCRIPTION:

3.1. STUDY DESIGN:

Experimental design: We propose to enroll a total of 48 CP patients who are scheduled for TP-IAT. This will be a 2:1 randomized, double blind, controlled study in which 32 patients receive islet cell transplantation together with intravenous AAT 60 mg/kg/week for 4 weeks, and 16 patients receive islets with intravenous 0.9% saline control in equivalent volume.

CP patients planning TP-IAT will receive an IRB approved consent form that describes the research study. Following signed consent, they will be enrolled and receive a baseline study visit. On the day of TP-IAT, an intravenous injection of AAT at the FDA approved dose of 60mg/kg or 0.9% normal saline will be infused before surgery. The autologous islet transplantation procedures will remain as routinely performed at MUSC. On the day of transplantation, the pancreas will be harvested and transferred to the Center for Cellular Therapy (CCT). Islets will be isolated and transplanted back to the patient via portal vein infusion. AAT or placebo will be given on day 0, 7, 14 and 21 days of islet transplantation.

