- Proportion of patients falling into one of the following levels of steatorrhea severity [time frame: day 75±14 and 365±14 after the transplant];
 1. No steatorrhea;
 2. Steatorrhea few times per week;
 3. Steatorrhea daily;
 4. Stool incontinence.
- Proportion of patients falling into one of the following malnutrition risk levels (poor prognosis, significant risk, increased risk, normal) according to pre-albumin level [time frame: day 75±14 and 365±14 after the transplant].
- Cumulative number of episodes of documented hypoglycemia (documented symptomatic; asymptomatic) [time frame: from day 75±14 to day 365±14 after the transplant].
- Cumulative number of diabetic ketoacidosis-related events [time frame: from day 75±14 to day 365±14 after the transplant].

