5.2. FORMULATION, DOSING, ADMINISTRATION AND EMERGENCY PRECAUTIONS

Prolastin-C is commercially available, and packed as a lyophilized powder and is ready to use after reconstitution with dilute (sterile water) that comes with the drug. Each pack contains 1000mg of AAT, and 20ml of dilutant. Both Prolastin-C and the dilutant should be stored at temperature not to exceed 25 (77 ° F). Reconstituted product from several vials may be pooled into an empty, sterile IV solution container by using aseptic technique. All the materials will have trial specific labels. The reconstitution should be used within 3 hours. The dosing will be administered at a rate of approximately 0.08ml/kg/min. The 60mg/kg dose takes approximately 15-30 minutes to infuse. If assigned to the placebo group, saline will be infused at the same volume and speed.

Each patient will receive 60mg/kg body weight if assigned in the AAT group. The first dose will be calculated based on the recipient's body weight during admission for transplant. The subsequent doses will be calculated based on the body weight recorded at study entry. The final dose for infusion will be rounded to the nearest whole vial dose, but must be within 10% of calculated dose.

The first infusion of the Investigational Product will start on the day of islet transplantation. Patient will receive 4 weekly doses of AAT or saline 7 ± 3 days apart.

The Investigational Product will be dispensed only by a qualified individual. Vital signs will be recorded within 30 minutes before the infusion, during infusion and 15 minutes after infusion. With each infusion, medical personnel will be available to treat subjects who experience difficulties. Emergency treatment such as 0.3ml to 0.5ml aqueous epinephrine (1:1000 dilution) subcutaneously and other resuscitative measure including oxygen, IV fluids, antihistamines, corticosteroids, vasopressors, and airway management, will be available in the infusion suite.

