6.3.6. Mixed meal tolerance test (MMTT)

MMTT tests will be performed at 75±14 and 365±14 days post-surgery. During the MMTT, patients will be asked to drink a special drink called 'BOOST', which will be given at a dose of 6 mL per kilogram body weight and contains a mixture of protein, fat and carbohydrates. Patient's blood will be drawn at 0, 15, 30, 60, 90, 120, 180 and 240 min after drinking the boost. In each time point, 4ml of blood will be collected, 2ml for measuring blood glucose, and 2ml to measure c-peptide levels. Samples will be sent to the blood lab for analysis.

6.3.7. Safety laboratory tests:

Laboratory tests will be performed before hospital discharge. These are standard of care tests done in all TP-IAT patients.

6.3.6. Vital signs: Blood pressure and heart rate will be measured before hospital discharge.

6.4. FOLLOW-UP VISITS:

Autologous islet transplant recipients will be followed up life-long in our center. For this study specifically, patients will be followed up till 12 months post-transplantation. They will have to attend 2 follow-up visits scheduled on day 75 ± 14 and 365 ± 14 days after the transplant, this can be combined with their routine returning visits.

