8.7. ASSESSMENT TIME WINDOWS

The Baseline visit should occur within 28 days of the screening visit. For all scheduled visits, allowable visit windows and study procedures are \pm 14 days from the calculated target day. The target day is defined as (Baseline Visit + 75 days) for the Day 75 target day, and (Baseline Visit + 365 days) for the Day 365 target day. If multiple measurements occur within the assessment time window, the measurement closest to the scheduled target day will be analyzed. Data collected outside of the specified time window will not be included in the primary analysis.

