8.10. SAFETY ANALYSES

Study subjects will be asked to report any and all AEs/new symptoms at any time from study enrollment until 52 weeks after study treatment, whether or not they attribute them to the study intervention or procedures. Subjects, who discontinue the study treatment regimen for any reason, including subjects who are treatment failures due to unable to return for some of the treatment injection(s) will be encouraged to attend the remaining visits for assessment of safety, secondary and pharmacokinetic endpoints.

To assess safety in this population, vital signs will be performed at each of the study visits. Additionally, medical history will be collected at screening and baseline and adverse events occurring after start of study therapy will be recorded.

Since the safety endpoints are primarily binary indicators for each subject (e.g. experiencing a particular AE during the 24-weeks post-treatment), their analyses will involve logistic regression models. For certain safety endpoints, it may be more appropriate for them to be analyzed using survival techniques, which are more suitable for time-to-event data than logistic regression. In such circumstances, Cox proportional hazards models will be used to compare treatment arms; however, should the proportionality assumptions not hold, alternative strategies (e.g. stratified analyses) will be used. The safety analyses will be conducted in the Safety Population.

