APPENDIX 1:

Study Phase	Screening	Treatment									Premature Withdrawal
Time points (days relative to transplant)	Screening	Baseline Before Surgery	Baseline After/ During Surgery	Day 1	Day 3	D7	D14	D21	D75	D365	
Visit#	1	2				3	4	5	6	7	
Visit Windows (days)						±2	±2	±2	±15	±15	
Informed Consent	x										
Medical and Diabetes History	x					x	x	x	x	x	x
Inclusion/Exclusion	x										
Immunoglobulin A (IgA)	x										
AAT infusion		x				x	x	x			
TP-IAT			x								
Inflammatory Cytokine Levels		x	x ³	x	x	x	x	x			
TAT, C3a, c-pep	x	x ¹ , x ²									
Serum AAT level		x ⁴									
Blood mononuclear RNA		x				x					
Blood DNA		x									
Plasma for proteomics, siRNA, etc		x				x					
MMTT -240min c-peptide and glucose									x	x	
Adverse Event Recording		x	x	x	x	x	x	x	x	x	x

- 1 Time 0 and 15 minutes after initiation of islet cell infusion in radiology suite.
- 2 Time 3 hours after initiation of islet cell infusion when participant is back in ICU.
- 3 Cytokine profile obtained 24 hours after initiation of islet cell infusion when participant is back in ICU.
- 4 AAT levels will be measured prior and 30mins after the first AAT infusion.

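### The hypoglycaemia and ketoacidosis counts in section 3.5.4 start at the day-75 visit, so they leave out the whole dosing period, and they make no allowance for follow-up time

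*Combined protocol and SAP*

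**What the plan says.** Two of the safety endpoints in section 3.5.4 are event counts with a restricted window. The ketoacidosis endpoint reads "Cumulative number of diabetic ketoacidosis-related events [time frame: from day 75±14 to day 365±14 after the transplant". The hypoglycaemia endpoint takes in episodes with and without symptoms and has the same start and end as the ketoacidosis count; its wording is "Cumulative number of episodes of documented hypoglycemia (documented symptomatic; asymptomatic) [time frame: from day 75±14 to day 365±14 after the transplant".

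No reason is given for starting at day 75. On dosing, section 3.1 states "AAT or placebo will be given on day 0, 7, 14 and 21 days of islet transplantation", and section 5.2 adds "Patient will receive 4 weekly doses of AAT or saline 7 ± 3 days apart".

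The two ends of the counting window match the two follow-up visits. Section 6.3.6 says "MMTT tests will be performed at 75±14 and 365±14 days post-surgery", and section 8.7 allows ± "14 days from the calculated target day". Appendix 1 shows ±15 days for the same two visits.

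Section 8.10 has patients report adverse events "at any time from study enrollment until 52 weeks after study treatment". It treats safety endpoints mostly as yes/no outcomes per patient, to be analysed by logistic regression, with Cox models where time to event suits better. It names no model for recurrent counts and no adjustment for time at risk. Section 8.2.3 puts everyone who consented and had surgery into the Safety Population.

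**The concern.** Treatment is given around the transplant, and section 2.1.1 attributes part of the islet loss to the period of harvest and after transplantation. If AAT changed the frequency of ketoacidosis or hypoglycaemia during exposure or in the following weeks, the two endpoints named for those events could not show it.

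The second issue is the denominator. A patient who dies, withdraws or is lost before the day-75 visit belongs to the Safety Population but has no counting window. The plan does not say whether that patient is scored zero or left out. Someone with an early ketoacidosis event who then leaves could appear event-free on this endpoint. A patient who leaves between day 75 and day 365 contributes a count over a shorter time, with nothing to mark it as shorter.

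**Working it through.** The plan states no figure on this point, so there is none to reproduce. The check is date arithmetic plus a reading of the analysis section.

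**Inputs.** Counting window: day 75±14 to day 365±14 after transplant (3.5.4). Doses: days 0, 7, 14, 21 (3.1), spaced 7±3 days (5.2). Visit tolerance: ±14 days (6.3.6, 8.7) or ±15 days (Appendix 1). Arms: 32 AAT and 16 placebo (3.1). Loss to follow-up: up to 10% (8.3).

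**1. Does the window touch dosing?**
- Earliest start: 75 − 14 = day 61.
- Last dose: day 21 nominal; latest under section 5.2 is 3 × (7 + 3) = day 30.
- Gap: 61 − 21 = 40 days, or 61 − 30 = 31 days at the least. With ±15 days it is 60 − 30 = 30 days.
- No dosing day is covered on any reading.

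**2. How much follow-up is uncounted?**
- Between 75 − 14 = 61 and 75 + 14 = 89 days.
- 61/365 = 17%; 75/365 = 21%; 89/365 = 24%.

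**3. How unequal is the window among completers?**
- Shortest: (365 − 14) − (75 + 14) = 351 − 89 = 262 days.
- Nominal: 365 − 75 = 290 days.
- Longest: (365 + 14) − (75 − 14) = 379 − 61 = 318 days.
- Ratio of longest to shortest: 318/262 = 1.21. With ±15 days: 320/260 = 1.23.
- Each extreme is about 10% from nominal (262/290 = 0.90; 318/290 = 1.10).

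**4. What does that do to the comparison of arms?** Assume visit dates are independent and uniform within ±14 days.
- SD of one visit date: 28/√12 = 8.1 days.
- SD of window length: 8.1 × √2 = 11.4 days, or 4% of 290.
- SE of the difference in arm means: 11.4 × √(1/32 + 1/16) = 3.5 days, or 3.5/290 = 1.2%.

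So unequal windows among completers are close to negligible at arm level unless visit timing differs by arm.

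**5. What could drop-out do?** Section 8.3 allows for 0.10 × 48 = 4.8 patients lost. If loss is alike in both arms, mean counts shrink in the same proportion and their ratio is little affected. As outer limits only: if all were lost before the window opened, all came from one arm, and all were scored zero, the mean count in that arm would be too low by 4.8/16 = 30% (placebo) or 4.8/32 = 15% (AAT). Nothing in the documents suggests loss this lopsided; the limits show why the denominator should be defined.

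**6. Does any analysis text cover these counts?** The mixed models in section 8.11 are for the endpoints of sections 3.5.2 and 3.5.3, not 3.5.4. The logistic and Cox models in section 8.10 do not analyse a cumulative count. A Cox model handles censoring for a first event only.

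**7. Effect of counting from day 0.** Completers' windows become 351 to 379 days, a ratio of 379/351 = 1.08 against 1.21 now.

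**The case against.** The strongest reply is that early events already have a home. The first endpoint in section 3.5.4 covers all AEs and SAEs with no day-75 start. Appendix 1 schedules AE recording from baseline through surgery, days 1, 3, 7, 14 and 21, and both later visits. Ketoacidosis that leads to or prolongs a hospital stay would meet the SAE definition in section 7.1.2 and go to the DSMB under section 7.2. Section 8.10 allows a particular AE to be compared between arms. This stands: a reader might infer that treatment-period ketoacidosis or hypoglycaemia goes unmonitored, and the documents do not support that.

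The late start may also be deliberate. An exploratory composite in section 3.5.3 uses the same period, and section 6.1.1 describes a post-operative insulin drip followed by individualised weaning, so early glucose events partly reflect insulin adjustment. That is a fair reason to keep the later window visible. It is not a reason to have no early count, and the plan does not state it.

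A reader might also infer that unequal windows make one arm look safer. Patients and treating investigators are blinded, and step 4 puts the chance imbalance at about 1.2%. Bias would need visit timing or drop-out to differ by arm.

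Finally, existing records may not support a full early hypoglycaemia count. The endpoint includes asymptomatic episodes, and nothing says that each low reading without symptoms is entered as an AE. This also stands, and it limits the fix.

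**Conclusion.** The point holds for the two named counts. They omit all dosing days and the first 61 to 89 days after transplant, and they have no defined denominator in a population that includes patients who leave early. The dates follow directly from sections 3.1, 3.5.4 and 5.2. The statement that window length is mainly noise rests on the assumption of uniform visit dates and on similar visit timing in blinded arms.

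The point should not be widened to the exploratory count of severe hypoglycaemia in section 3.5.3. That count has no stated window, so the documents do not show it starting late.

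This is a low-priority improvement in a 48-patient proof-of-concept trial where section 8.3 calls all testing exploratory. It brings the exposure period into the comparison of these two endpoints and stops drop-outs being treated as event-free for time when they were not observed.

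**What to change.** 1. Report ketoacidosis-related events from day 0 to the day-365 visit using the existing AE/SAE records. Show day 0 to the day-75 visit and the day-75 visit to the day-365 visit separately, so that the present window is still reported.
2. Do the same for documented hypoglycaemia as far as existing records allow. Label the early count as AE-reported, because asymptomatic episodes may be under-recorded.
3. Analyse both as rates: Poisson or negative binomial with log observed follow-up time as offset, or exact Poisson if events are sparse. State that patients who leave contribute time only up to their last observation.
4. Reconcile the ±14 days in sections 3.5.4, 6.3.6 and 8.7 with the ±15 days in Appendix 1.

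The cost is endpoint and analysis wording, with no new data collection for ketoacidosis. For hypoglycaemia, the sponsor should first confirm what was recorded before day 75. The downside is that early events partly reflect post-operative insulin adjustment and that early hypoglycaemia may be less completely recorded; the split by period keeps both visible.

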4. STUDY POPULATION

CP patients scheduled for TP-IAT will be enrolled in this study. Our recruitment goal is to reach a total of 48 patients, each randomized to receive either standard of care (SOC) plus placebo or SOC with AAT after consent.

4.1. Inclusion criteria

- Patients scheduled for total pancreatectomy and islet autotransplantation
- Age \geq 18 years
- Diabetes free before surgery

4.2. Exclusion criteria

- Patients who are under immunosuppression (eg. more than 5 mg prednisone use of another immunosuppressive drug including but not limited to methotrexate, cyclosporine, tacrolimus, azathoprine, sirolimus, or rituxan).
- Patients who have had puestow or frey pancreatic surgery
- Patients who have Immunoglobulin A (IgA) deficiency, known antibodies against IgA, or individuals with a history of severe immediate hypersensitivity reactions, including anaphylaxis to Alpha₁-proteinase inhibitor products (allergic to AAT)

4.3. Assignment of patient number

Once patient is determined eligible for the study, and randomized into a group, they will be assigned a unique number for the study. This patient is then evaluable under intention to treat analysis as defined in the statistical plan.

5. INVESTIGATIONAL PRODUCT

5.1. Investigational product:

5.1.1. Prolastin-C (Grifols) is human alpha-1 proteinase inhibitor (AAT) that is indicated for chronic augmentation and maintenance therapy in adults with emphysema due to deficiency of alpha1-proteinase inhibitor. Prolastin-C is approved in the US, Canada, Columbia, and Argentina for 60 mg/kg weekly IV administration for augmentation therapy in patients with severe AATD and clinically evident emphysema. It is a sterile, stable, lyophilized preparation of purified human protein inhibitor. Prolastin-C is prepared from pooled human plasma from healthy donors by modification and refinements of the Cohn cold ethanol plasma fractionation technique followed by a purification process. Prolastin-C contains small amounts of other plasma proteins, which may include IgA, haptoglobin, alpha1-acid glycoprotein, lipoprotein A-1, and albumin. Reconstituted Prolastin-C contains no preservatives, has a pH of 6.6 to 7.4, and is to be administered by the IV route.

5.1.2 Placebo

Placebo used in this study will be 0.9% Sodium Chloride for Injection, USP.

5.2. FORMULATION, DOSING, ADMINISTRATION AND EMERGENCY PRECAUTIONS

Prolastin-C is commercially available, and packed as a lyophilized powder and is ready to use after reconstitution with dilute (sterile water) that comes with the drug. Each pack contains 1000mg of AAT, and 20ml of dilutant. Both Prolastin-C and the dilutant should be stored at temperature not to exceed 25 (77 ° F). Reconstituted product from several vials may be pooled into an empty, sterile IV solution container by using aseptic technique. All the materials will have trial specific labels. The reconstitution should be used within 3 hours. The dosing will be administered at a rate of approximately 0.08ml/kg/min. The 60mg/kg dose takes approximately 15-30 minutes to infuse. If assigned to the placebo group, saline will be infused at the same volume and speed.

Each patient will receive 60mg/kg body weight if assigned in the AAT group. The first dose will be calculated based on the recipient's body weight during admission for transplant. The subsequent doses will be calculated based on the body weight recorded at study entry. The final dose for infusion will be rounded to the nearest whole vial dose, but must be within 10% of calculated dose.

The first infusion of the Investigational Product will start on the day of islet transplantation. Patient will receive 4 weekly doses of AAT or saline 7 ± 3 days apart.

The Investigational Product will be dispensed only by a qualified individual. Vital signs will be recorded within 30 minutes before the infusion, during infusion and 15 minutes after infusion. With each infusion, medical personnel will be available to treat subjects who experience difficulties. Emergency treatment such as 0.3ml to 0.5ml aqueous epinephrine (1:1000 dilution) subcutaneously and other resuscitative measure including oxygen, IV fluids, antihistamines, corticosteroids, vasopressors, and airway management, will be available in the infusion suite.

5.3. DRUG ACCOUNTABILITY

Under Title 21 of the Code of Federal Regulation (21CFR{312.62 Investigator recordkeeping and record retention.), an investigator is required to maintain adequate records of the drug preparation and disposition, and maintain adequate and accurate case histories that record all observations and other data pertinent to the investigation.

Records for receipt, storage, use and disposition will be maintained by the unblinded study coordinator. A drug dispensement log including the identification of each subject, date and quantity of drug used will be kept current for each subject. Any drug accidentally or deliberately destroyed will be recorded as well.

5.4. CRITERIA FOR SCHEDULE ADJUSTMENT, DOSE-MODIFICATION, DISCONTINUATION OF INVESTIGATIONAL DRUG.

5.4.1. No schedule adjustment and/or dose modification is foreseen, except for discontinuation of drug as detailed below:

5.4.2. Criteria for discontinuation of Investigational Product

Any subject may voluntarily withdraw (ie, reduce the degree of participation in the study) consent for continued participation and data collection. The reason for withdrawal will be recorded on the appropriate CRF. Patients who discontinue the treatment with the investigational drug will not be withdrawn from the study by default, but will complete observations as per the protocol, unless otherwise they withdraw their consent.

Discontinuation (ie, complete withdrawal from study participation) may be due to dropout (ie, active discontinuation by subject) or loss to follow-up (ie, discontinuation by subject without notice or action), or death. Additionally, the investigator and sponsor have the discretion to discontinue any subject from the study if, in their judgment, continued participation would pose an unacceptable risk for the subject. Subjects meeting the definition for intent-to-treat who are prematurely terminated from study treatment will not be replaced.

5.5. STUDY STOPPING RULES

Study enrollment will be suspended pending review of all pertinent data by the institutional review board (IRB), and the Data Safety Monitoring Board (DSMB), if any of the following occurs:

- Any unexpected fatal or life-threatening AE possibly related to the use of the Investigational drug.
- Any event(s) the protocol chair determines will require full DSMB review.
- The DSMB recommends termination of protocol enrollment based on review of the data and evidence that such action is necessary.

6. STUDY PROCEDURE AND ASSESSMENTS:

